11.2.3 Listing of Adverse Events

The following additional summaries of adverse events will be prepared.

- List of subject numbers associated with each PT for all TEAEs
- List of subject numbers associated with each PT for all TEAEs assessed by the investigator as having Reasonable Possibility of Being Related.
- Listing of all serious adverse events
- Listing of all adverse events that led to discontinuation of study drug
- Listing of all fatal adverse events
- Listing of all deaths

11.3 Analysis of Laboratory Tests

Analyses will be performed on the following continuous laboratory variables:

Hematology	Clinical Chemistry	Urinalysis
Hematocrit	Blood urea nitrogen (BUN)	Specific gravity
Hemoglobin	Creatinine	pH
Red blood cell (RBC) count	Total bilirubin	
White blood cell (WBC) count	Albumin	
Neutrophils	Aspartate aminotransferase (AST)	
Bands (if detected)	Alanine aminotransferase (ALT)	
Lymphocytes	Alkaline phosphatase	
Monocytes	Sodium	
Basophils (if detected)	Potassium	
Eosinophils (if detected)	Calcium	
Platelet count (estimate not acceptable)	Inorganic phosphate	
Mean corpuscular volume (MCV)	Uric acid	
Mean corpuscular hemoglobin concentration (MCHC)	Cholesterol	
Prothrombin time (PT)	Total protein	
Activated partial thromboplastin time (aPTT)	Glucose	
PT/INR (Prothrombin Time/International Normalized Ratio)	Triglycerides	
	Bicarbonate/Carbon Dioxide (CO ₂) Chloride	

11.3.1 Analysis of Mean Changes for Laboratory Tests

Analyses of mean change from baseline to each double-blind visit value and to the minimum, maximum and final double-blind value will be presented for each continuous hematology, chemistry and urinalysis variable. Analyses of mean change from final double-blind value to final post-treatment value will also be presented for each continuous hematology, chemistry and urinalysis variable.

For each mean change analysis, the mean and median change will be presented for each treatment group. The mean change for each ABBV-8E12 dose group will also be compared to the mean change for the placebo group using an ANOVA with treatment as

the factor. *P* values and 95% confidence intervals will be calculated based on pairwise contrasts within the ANOVA.

11.3.2 Shifts Between Normal and Abnormal for Laboratory Tests

Laboratory observations will be categorized as normal, low, or high relative to the reference (normal) range associated with the laboratory that performed the assay. For each hematology and chemistry variable with a reference range, shift tables will be prepared for shifts from baseline to lowest, highest and final value during the entire study for each treatment group and ABBV-8E12 overall. No comparisons of treatment groups will be performed. The tables will present:

- The numbers and percentages of subjects with low or normal observations at baseline who have a high observation at any post-baseline visit
- The numbers and percentages of subjects with normal or high observations at baseline who have a low observations at any post-baseline visit
- The numbers and percentages of subjects with low or normal observations at baseline who have a high observation at the final visit
- The numbers and percentages of subjects with normal or high observations at baseline who have a low observations at the final visit

11.3.3 Potentially Clinically Significant Laboratory Values

Criteria for potentially clinically significant (PCS) values have been predefined for selected laboratory variables as outlined in [Appendix A](#). For each variable, a summary of the number and percentage of subjects in each treatment group who have at least one double-blind observation that meets the PCS criteria and is more extreme than their baseline value will be provided. A listing will also be prepared that will include, for each variable, all observations for each subject that meet the PCS criteria for that variable at any time during the study. No comparisons of treatment groups will be performed.

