8.1.6.2 Analysis of Laboratory Tests

Change from baseline to each double-blind visit value and to the minimum, maximum and final double-blind value will be presented for each continuous hematology, chemistry and urinalysis parameter. Treatment differences between each ABBV-8E12 dose group and placebo in change from baseline to minimum, maximum and final clinical laboratory evaluation will be analyzed using one-way ANOVA with treatment as the main effect.

For each treatment group, shift tables will be generated showing the number and percentage of subjects with low, normal, high and missing values at baseline and final observation based on the reference ranges provided by each laboratory.

The number and percentage of subjects in each treatment group who have values meeting predefined criteria for potentially clinically significant values (definitions will be provided in the SAP) at any time after the first dose of study drug and no more than 20 weeks after the last dose of study drug or before the first dose in the planned extension study will be summarized separately for hematology and chemistry variables.

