8.1.6.3 Analysis of Vital Signs and Weight

Vital sign variables include pulse, systolic blood pressure, diastolic blood pressure, body temperature, weight, and body mass index (BMI).

Change from baseline to each double-blind visit value and to the minimum, maximum and final double-blind value will be presented for each vital sign and weight variable and analyzed using one-way ANOVA with treatment as the main effect.

The number and percentage of subjects in each treatment group who have values meeting predefined criteria for potentially clinically significant values (definitions will be provided in the SAP) at any time after the first dose of study drug and no more than 20 weeks after the last dose of study drug or before the first dose in the planned extension study will be summarized.

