8.1.6.4 Analysis of ECG Variables

ECG variables include heart rate, PR, QRS, QT and QTcF intervals. Change from baseline to final double-blind value will be presented for each ECG parameters and analyzed by a one-way ANOVA with treatment as the main effect.

The number and percentage of subjects in each treatment group who have values meeting predefined criteria for potentially clinically significant values (defined in the SAP and DMC charter) at any time after the first dose of study drug will be summarized.

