11.0 Safety Analysis

11.1 General Considerations

All safety analyses will be performed on the safety dataset. Unless otherwise specified, treatment group differences in safety parameters are evaluated using two-sided test at the significance level of 0.050. When statistical tests are performed, the comparisons will be between each ABBV-8E12 dose and placebo. With the exception of adverse events, all safety assessments that are taken no more than 45 days after the last dose of study drug infusion will be included in the safety evaluation of the Double-blind Treatment Period. All safety assessments that are taken more than 45 days but no more than 20 weeks after the last dose of study drug infusion will be included in the safety evaluation for the Post-Treatment Follow-Up Period.

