11.2 Analysis of Adverse Events

All adverse events will be coded using the most current version of the Medical Dictionary for Regulatory Activities (MedDRA). A treatment-emergent adverse event (TEAE) is defined as any adverse event that begins or worsens in severity on or after the first study drug dose date and no more than 20 weeks after the last study drug dose date.

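### The SAP's by-arm counts of potentially clinically significant laboratory, vital-sign and ECG values stop 45 days after the last dose; the protocol's windows run longer and include the Week 104 visit.

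*SAP*

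**What the plan says.** **Protocol.** Section 8.1.6.2 summarises by treatment group the subjects with PCS laboratory values "at any time after the first dose of study drug and no more than 20 weeks after the last dose of study drug", or up to the first extension dose. Section 8.1.6.3 uses the same window for vital signs and weight: "no more than 20 weeks after the last dose of study drug or before the first dose in the planned extension study will be summarized". Section 8.1.6.4 counts PCS ECG values "at any time after the first dose of study drug will be summarized", with no upper limit.

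**SAP.** Section 11.3.3 gives by treatment group the subjects with "at least one double-blind observation that meets the PCS criteria", on the further condition that the value lies beyond the subject's baseline. Sections 11.4.2 (vital signs and weight) and 11.5.2 (ECG) use the same construction. Section 11.1 defines the double-blind evaluation, adverse events excepted, as "all safety assessments that are taken no more than 45 days after the last dose of study drug infusion". Assessments after 45 days and up to 20 weeks go to a separate post-treatment follow-up evaluation, but none of the three PCS sections defines a by-arm count for that period. Adverse events keep the longer window: Section 11.2 treats an event as treatment-emergent if it starts or worsens "no more than 20 weeks after the last study drug dose date".

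**Section 14 of the SAP** says in general terms that changes from the protocol's planned analyses entered version 1.0, and itemises the changes in versions 2.0 and 3.0. The shorter PCS window is not among them.

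**The concern.** The protocol specifies a count by treatment group over one window, and the SAP produces it over a shorter one without saying so. What matters is whether any scheduled measurement falls between the two limits. If none did, the difference would be only one of wording. If a visit does, threshold-crossing values from it are missing from the table that the protocol says will contain them.

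Long-term safety is one of the two primary objectives. The subjects concerned are those who stop treatment early, decline the extension or do not qualify for it, because only they have post-treatment visits in this study. The SAP also applies two windows to related safety data: a late laboratory abnormality reported as an adverse event is tabulated by arm to 20 weeks, while the same value as a PCS observation is not counted after 45 days.

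**Working it through.** **Inputs.** From the Study Activities table (Protocol Appendix C, SAP Table 2): Dose 23 on Day 617, Dose 24 on Day 645, Week 96 on Day 673, Week 104 on Day 729, Week 112 on Day 785. Follow-up visits come about 8 and 16 weeks after the completion or premature discontinuation (PD) visit, with a window of ±4 days. Limits after the last dose: 45 days (SAP 11.1); 20 weeks = 140 days (Protocol 8.1.6.2 and 8.1.6.3).

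**Reproducing the plan's own figure.** The protocol gives follow-up as about 20 weeks after the last administration. 785 − 645 = 140 days, and 140 / 7 = 20.0 weeks. The schedule agrees.

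**Subjects who receive Dose 24.** Days after last dose = visit day − 645.

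| Visit | Days after last dose | Laboratory, vital signs, ECG scheduled? | SAP PCS count (≤ 45) | Protocol laboratory and vital-sign window (≤ 140) |
|---|---|---|---|---|
| Week 96 | 673 − 645 = 28 | yes | in | in |
| Week 104 | 729 − 645 = 84 | yes | out | in |
| Week 112 | 785 − 645 = 140 | no | – | – |

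Week 112 has drug and anti-drug antibody samples, concomitant medication and adverse events only. Week 104 is therefore the single post-treatment visit with these three assessments. SAP 6.2 assigns it to the post-treatment window (more than 45 days after the last dose).

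**Early discontinuers.** The interval from last dose to PD visit is not fixed by the documents; assume 0 to 28 days. The first follow-up visit then falls at

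- earliest: 0 + 56 − 4 = 52 days
- latest: 28 + 56 + 4 = 88 days

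This is beyond 45 and within 140 throughout. The lower end does not depend on the assumed interval, since even a PD visit on the day of the last dose gives 52 days. The upper end would pass 140 only if the PD visit came more than 80 days after the last dose (80 + 56 + 4 = 140).

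**A further case.** A subject who misses Dose 24 but attends Week 96 has that visit at 673 − 617 = 56 days after the last dose. Week 96 then also leaves the SAP's PCS count, whether or not the subject enters the extension.

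**Do other outputs supply the missing count?**

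- PCS listings (SAP 11.3.3, 11.4.2, 11.5.2): all qualifying observations at any time in the study, by subject, with no number or percentage by arm.
- Change from final double-blind to final post-treatment value (SAP 11.3.1, 11.4.1, 11.5.1): by arm with an ANOVA against placebo, but on means, with no threshold.
- Shift tables (SAP 11.3.2): by arm over the entire study, but against laboratory reference ranges and only for hematology and chemistry.
- Treatment-emergent adverse events (SAP 11.2.2): by arm to 20 weeks, but by MedDRA term, and only for findings reported as events.

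None is a by-arm count against PCS thresholds that includes Week 104.

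**The case against.** The strongest reply is that little is lost. PCS counts are descriptive: SAP 11.3.3, 11.4.2 and 11.5.2 each rule out treatment-group comparisons. Where the SAP does test arms on these variables, in the mean-change analyses, post-treatment values are included. Protocol 5.3.1.1 requires the investigator either to report an adverse event for a PCS laboratory value or to document why not, so some late values reach the adverse-event tables. Separating on-treatment from post-treatment data is also a recognised approach. And only subjects who do not enter the extension have a Week 104 visit.

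All of this stands, and it limits the point to one type of table. It does not remove the conflict, because the protocol specifies that table over the longer window and the SAP has no post-treatment PCS count by arm.

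Several stronger readings are tempting, and the documents do not support them:

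- That a visit drops out of the comparison between arms. No PCS comparison is planned, and the post-treatment ANOVA remains.
- That post-treatment safety data are discarded, or survive only in listings. They are used in the outputs listed in the working.
- That Week 104 is the only post-treatment safety visit. Adverse events are also collected at Week 112.
- That the protocol sets 20 weeks for ECG. It sets no upper limit there.
- That early stoppers are the subjects most likely to show late abnormalities. This is a reasonable worry, but neither document shows it.
- That the change was concealed. Section 14 covers version 1.0 with one general sentence, so its silence shows only that the change is not named or explained.

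**Conclusion.** The SAP departs from the protocol. For subjects not entering the extension, all scheduled Week 104 laboratory, vital-sign and ECG values fall outside the by-arm PCS counts, although the protocol's windows include them. Week 96 values are lost in the same way when Dose 24 is missed.

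The importance is minor. No hypothesis test changes, and no error rate or power is involved. The number of subjects and of PCS values affected cannot be derived from the documents, because it depends on how many subjects do not enter the extension and on what is observed.

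The conclusion rests on the scheduled visit days and on reading the SAP's double-blind observation by the 45-day definition in its Section 11.1, which its Section 6.2 windows confirm. For early discontinuers, inclusion in the 140-day window also assumes a PD visit no more than 80 days after the last dose.

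**What to change.** In SAP 11.3.3, 11.4.2 and 11.5.2, add a by-arm PCS count over the protocol's window and keep the double-blind count beside it:

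- laboratory and vital signs: first dose to 20 weeks after the last dose, cut at the first extension dose;
- ECG: any time after the first dose, as the protocol states.

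A separate by-arm PCS count for the post-treatment period would serve equally and would keep on-treatment and post-treatment values apart. Either way, name the two windows and the reason for them in SAP Section 14.

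The cost is SAP wording, a changed date filter and one more column or table; no new data are needed. Weight gains no scheduled observations, because it is not measured at Week 104.

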11.4 Analysis of Vital Signs and Weight

Vital sign variables include: diastolic blood pressure, systolic blood pressure and pulse rate and body temperature. Weight variables include weight and BMI.

11.4.1 Vital Sign and Weight Mean Changes

Diastolic blood pressure, systolic blood pressure and pulse will be analyzed separately. Analyses of mean change from baseline to each double-blind visit value and to the minimum, maximum and final double-blind value will be presented for each vital sign and weight variable. Analyses of mean change from final double-blind value to final post-treatment value will also be presented for each vital sign and weight variable.

For each mean change analysis, the mean and median change will be presented for each treatment group. The mean change for each ABBV-8E12 dose group will also be compared to the mean change for the placebo group using an ANOVA with treatment as the factor. *P* values and 95% confidence intervals will be calculated based on pairwise contrasts within the ANOVA.

11.4.2 Potentially Clinically Significant Vital Sign and Weight Values

Criteria for potentially clinically significant values have been predefined for selected vital sign and weight variables as outlined in [Appendix A](#). For each variable, a summary of the number and percentage of subjects in each treatment group who have at least one double-blind observation that meets the PCS criteria and is more extreme than their baseline value will be provided. A listing will also be prepared that will include, for each variable, all observations for each subject that met the PCS criteria for that variable at any time during the study. No comparisons of treatment groups will be performed.

11.5 Analysis of Electrocardiogram (ECG) Variables

Electrocardiogram (ECG) variables include: heart rate (HR), PR interval, QRS interval, uncorrected QT interval, and QT interval corrected for heart rate using Fridericia's formula (QTcF).

11.5.1 ECG Mean Changes

Analyses of mean change from baseline to each double-blind visit value and to the minimum, maximum and final double-blind value will be presented for each ECG variable. Analyses of mean change from final double-blind value to final post-treatment value will also be presented for each ECG variable.

For each mean change analysis, the mean and median change will be presented for each treatment group. The mean change for each ABBV-8E12 dose group will also be compared to the mean change for the placebo group using an ANOVA with treatment as the factor. *P* values and 95% confidence intervals will be calculated based on pairwise contrasts within the ANOVA.

11.5.2 Potentially Clinically Significant ECG Values

Criteria for potentially clinically significant values have been predefined for selected ECG variables as outlined in [Appendix C](#). For each variable, a summary of the number and percentage of subjects in each treatment group who have at least one double-blind observation that meets the PCS criteria and is more extreme than their baseline value will be provided. Listings will also be prepared to include all observations for each variable for each subject that meet the PCS criteria for that variable at any time during the study. No comparisons of treatment groups will be performed.

11.6 Analysis for Other Safety Variables

11.6.1 Columbia-Suicide Severity Rating Scale (C-SSRS)

Number and percentage of subjects in the following categories will be summarized for each treatment group and ABBV-8E12 Overall by visit and for the entire study:

- Answered 'Yes' to each C-SSRS item
- Had suicidal ideation (defined as answering 'Yes' to one or more suicidal ideation items)
- Had suicidal ideation only (defined as answering 'Yes' to one or more suicidal ideation items and answering 'No' to all suicidal behavior items)
- Had suicidal behavior (defined as answering 'Yes' to one or more suicidal behavior items)
- Had suicidal ideation or behavior (defined as answering 'Yes' to one or more suicidal ideation or behavior items)

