5.2.2 Exclusion Criteria

A subject will not be eligible for study participation if he/she meets any of the following criteria:

1. Subject has any visual, auditory or other impairment that in the Investigator's opinion would preclude collection of outcome measures.
2. Subject has any contraindication to or inability to tolerate brain MRIs (e.g., a pacemaker or any other implanted device or condition that would preclude proximity to a strong magnetic field).
3. Subject has any contraindication to or inability to tolerate a PET scan (includes current or recent participation in any procedures involving radioactive agents such that the total radiation dose exposure to the subject in any given year would exceed the local country limits of annual and total dose).
4. Subject enrolled in Cohort 1 has any contraindications to or inability to tolerate lumbar punctures (e.g., use of anticoagulant medications such as warfarin and inability to temporarily cease use of such therapy for a limited duration surrounding lumbar punctures).
5. Subject has evidence of any other clinically significant neurological disorder other than Early AD, including but not limited to:
 - Parkinson's disease
 - vascular dementia
 - significant cerebrovascular abnormalities
 - frontal-temporal dementia

- Huntington's disease
 - normal pressure hydrocephalus
 - brain tumor
 - progressive supranuclear palsy
 - seizure disorder
 - subdural hematoma
 - multiple sclerosis
 - history of significant head trauma followed by persistent neurologic deficits
 - known structural brain abnormalities
6. Subject has a screening MRI scan, interpreted by a radiologist with evidence of infection, infarction (including multiple lacunas in a critical memory structure), or other focal lesions.
 7. Subject has a history of or currently has schizophrenia, schizoaffective disorder or bipolar disorder according to DSM-V or ICD-10 criteria.
 8. In the opinion of the investigator, the subject has any clinically significant or uncontrolled medical or psychiatric illness, or has had an infection requiring medical intervention in the past 30 days.
 9. Subject has significant current suicidal ideation within one year prior to Screening as evidenced by answering "yes" to questions 4 or 5 on the suicidal ideation portion of the Columbia-Suicide Severity Rating Scale (C-SSRS) completed at Screening or a history of suicidal attempts within the last 2 years.

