The RBANS has been shown to be effective at both detecting and characterizing dementia of different etiologies. The Delayed Memory domain has been shown to be particularly sensitive to discriminating mild cognitive impairment (MCI) due to AD from controls, and also is predictive of cerebral amyloid burden. The RBANS has been translated into over 25 different languages, with extensive clinical validity data from a wide variety of geographic regions. The RBANS will be administered to the patient at the times indicated in [Table 4](#).

University of California's Performance Based Skills Assessment, Brief Version (UPSA – Brief)²⁹

The UPSA-Brief is a performance-based instrument which uses a series of tasks and role-play scenarios to evaluate a person's functional capacity in two areas of basic living skills (i.e., financial skills and communication skills). The UPSA-Brief will be administered to the patient at the times indicated in [Table 4](#).

Columbia-Suicide Severity Rating Scale³⁰

The C-SSRS is a systematically administered instrument developed to track suicidal adverse events across a treatment study. The instrument is designed to assess suicidal behavior and ideation, track and assess all suicidal events, as well as the lethality of attempts. Additional features assessed include frequency, duration, controllability, reason for ideation, and deterrents. The C-SSRS is considered a low-burden instrument as it typically takes less than 5 minutes to administer. The C-SSRS questionnaire will be administered at the time points indicated in the Study Activities Table ([Appendix C](#)).

Any subject noted to have suicidal ideation with plan within the prior month, either via answering "yes" to questions 4 or 5 to the suicidal ideation portion of the C-SSRS or via

clinical interview, will be evaluated immediately by the study physician. The AbbVie TA MD will also be informed. Appropriate steps will be taken to protect the subject, including but not limited to possible discontinuation from the study and referral for appropriate psychiatric care. Any such subject at Screening or on Day 1 will also be excluded from the study.

Digital Clock Drawing Test (dCDT)

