8.1.6.5 Analysis of C-SSRS

Number and percentage of subjects in the following categories will be summarized for each treatment group by visit and for the entire study:

- Answered 'Yes' to each C-SSRS item
- Had suicidal ideation (defined as answering 'Yes' to one or more suicidal ideation items)
- Had suicidal ideation only (defined as answering 'Yes' to one or more suicidal ideation items and answering 'No' to all suicidal behavior items)
- Had suicidal behavior (defined as answering 'Yes' to one or more suicidal behavior items)
- Had suicidal ideation or behavior (defined as answering 'Yes' to one or more suicidal ideation or behavior items)

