Randomization Visit). At the computation level, the value of "baseline" for an efficacy or safety assessment is determined using the Rx Day associated with the visit. Namely, baseline value is determined by taking the last non-missing observation obtained before the time of first dosing on Rx Day 1. If an SAE occurs on the first dosing day, the event will be reported as a post-baseline event and the related safety assessments will be considered post-baseline data as well.

Definition of Analysis Windows

To perform longitudinal data analysis, observations that are obtained after the first day of study drug administration will be assigned to an analysis "week" associated with the Rx Days that are corresponding to the observations. Unless otherwise specified, efficacy observations and safety observations no more than 45 days after the last dose of study drug will be included in analyses for the double-blind period. Safety observations later than 45 days, but no more than 20 weeks, after the last dose of study drug will be included for the post-treatment follow-up period safety analysis. The intervals presented below for each scheduled visit (Rx Days X through Y) include both Rx Days X and Y. The nominal day for each scheduled visit is defined in "Days of Study Activities" row in [Table 2](#).

For measurements that are planned to be collected during the double-blind treatment period at Weeks 24, 48, 72 and 96, i.e., CDR, RBANS, ADAS-Cog-14, MMSE, FAQ and NPI, observations will be mapped to an analysis "week" according to the following windows defined by Rx day.

- Week 24 Rx Days 2 through 252
- Week 48 Rx Days 253 through 420
- Week 72 Rx Days 421 through 588
- Week 96 Rx Days > 588

For measurements that are planned to be collected during the double-blind treatment period at Weeks 48 and 96, i.e., UPSA-Brief, ADCS-CGIC-MCI and ADCS-MCI-ADL-

24, observations will be mapped to an analysis "week" according to the following windows defined by Rx day.

- Week 48 Rx Days 2 through 504
- Week 96 Rx Days > 504

For measurements that are planned to be collected during the double-blind treatment period at Weeks 4, 8, 12, 16, 20, 24, 28, 32, 36, 40, 44, 48, 52, 56, 60, 64, 68, 72, 76, 80, 84, 88, 92 and 96, i.e., body weight, observation will be mapped to an analysis "week" according to the following windows defined by Rx day.

- Week 4 Rx Days 2 through 42
- Week 8 Rx Days 43 through 70
- Week 12 Rx Days 71 through 98
- Week 16 Rx Days 99 through 126

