11.6.3 Summary of MRI Safety Evaluations

MRI safety evaluations will be summarized and compared between each ABBV-8E12 dose and placebo based on MRI evaluations in the double-blinded period. The summaries include number and percentage of subjects with presence and severity of baseline and post baseline MRI findings of cerebral edema, microhemorrhages, and severe white matter disease as defined by a score of 3 on Age-Related White Matter Changes (ARWMC) scale and other structural abnormalities. Descriptive statistics (mean, median, minimum, maximum) of number of new microhemorrhages or new lesions in the double-blind period will be presented. Listing of subjects with post-baseline MRI findings will be provided. No comparison will be performed for MRI safety summary.

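### The C-SSRS summary ignores each subject's own pre-dose answers, so its item 1-3 and composite ideation rows cannot separate persistent from new or worsened ideation

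*SAP*

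**What the plan says.** SAP Section 11.6.1 lists five C-SSRS categories: a yes to each item, ideation, ideation only, behaviour, and ideation or behaviour. The ideation row reads "Had suicidal ideation (defined as answering 'Yes' to one or more suicidal ideation items". The ideation-only row also requires a no to every behaviour item. No row refers to the subject's earlier answers, and the section plans no shift table or listing. Protocol Section 8.1.6.5 has the same five categories, "summarized for each treatment group by visit and for the entire study".

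A pre-dose value exists. The C-SSRS is given at Screening and before the first infusion (protocol Table 4 and Appendix C), and SAP Section 6.2 defines a baseline for safety data: "baseline value is determined by taking the last non-missing observation obtained before the time of first dosing on Rx Day 1". Section 11.6.1 does not use it.

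Other planned safety summaries do look back to pre-dose status:

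- A treatment-emergent event is "any adverse event that begins or worsens in severity on or after the first study drug dose date" (SAP Section 11.2).
- The laboratory, vital-sign and ECG flag counts require "at least one double-blind observation that meets the PCS criteria and is more extreme than their baseline value" (worded in SAP Section 11.3.3 and repeated in 11.4.2 and 11.5.2).
- The MRI summary covers baseline and post-baseline findings and the "number of new microhemorrhages or new lesions in the double-blind period" (SAP Section 11.6.3).

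At entry, exclusion 9 names a yes to "questions 4 or 5 on the suicidal ideation portion of the Columbia-Suicide Severity Rating Scale (C-SSRS) completed at Screening" and suicide attempts in the last 2 years. The C-SSRS text in protocol Section 5.3.1.1 adds ideation with a plan in the prior month: "Any such subject at Screening or on Day 1 will also be excluded from the study".

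**The concern.** Long-term safety is a primary objective. For a drug given over 96 weeks, the question this table should answer is how many subjects in each arm developed suicidal ideation, or saw it worsen, after dosing began. The planned rows answer a different question: how many gave a yes, whether or not they had done so before dosing.

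The two differ only if people with ideation can enter. They can at items 1-3, because the entry rules stop at items 4-5, plans and recent attempts. They can also stay: the C-SSRS trigger for discontinuation in protocol Section 5.4.1 is again item 4 or 5, alongside the investigator's judgment of risk. At stake is how a reader interprets a handful of cases per arm.

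**Working it through.** **Logical check.** Take three subjects: A answers yes to item 1 before dosing and at every later visit; B first answers yes to item 1 after dosing; C moves from item 1 before dosing to item 3 after it. All three count once in the ideation row. A and B also share the item 1 row. The item 3 row does not show where C started. By-visit counts are group totals, so within-subject change cannot be recovered from them.

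**What the whole-study summary covers.** The text does not say that pre-dose answers are left out. The C-SSRS windows in SAP Section 6.2 start on Rx Day 2, so the charitable reading is post-dose only, and it is used here. If pre-dose answers were included, the mixing would be greater.

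**Size.** The plan gives no figure to reproduce. The following is an illustration under assumed rates.

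- From the documents: 100 subjects per arm (SAP Section 4.3).
- Assumed: new on-treatment ideation x = 2% on placebo and 4% on active, a true ratio of 2.0; pre-dose item 1-3 ideation p0 = 1%, 2% or 5% in each arm; share persisting q = 0.5.
- Row rate = p0·q + (1 − p0)·x.
- Share not new = p0·q / row rate.

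For p0 = 2%, placebo is 0.02 × 0.5 + 0.98 × 0.02 = 0.0296 and active is 0.02 × 0.5 + 0.98 × 0.04 = 0.0492. The ratio is 1.66 and the difference 1.96 points.

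| p0 | Placebo | Active | Ratio | Difference (points) | Not new, placebo / active |
|---|---|---|---|---|---|
| 0% | 2.00% | 4.00% | 2.00 | 2.00 | 0% / 0% |
| 1% | 2.48% | 4.46% | 1.80 | 1.98 | 20% / 11% |
| 2% | 2.96% | 4.92% | 1.66 | 1.96 | 34% / 20% |
| 5% | 4.40% | 6.30% | 1.43 | 1.90 | 57% / 40% |

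With q from 0.25 to 0.75 the ratio runs from 1.89 to 1.73 (p0 = 1%), 1.80 to 1.57 (2%) and 1.60 to 1.34 (5%).

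**Noise.** Let persistent cases per arm be Binomial(100, p0·q). Two arms then differ by 2 or more such cases with probability 0.118, 0.259 or 0.484 for p0 = 1%, 2% or 5%. For comparison, in a table of new cases only, with 2% in both arms and no drug effect, the same probability is already 0.43. At 2% against 4%, the SD of the difference in new cases is √[100 × (0.02 × 0.98 + 0.04 × 0.96)] = 2.41 subjects. Putting the row rates above into the same formula gives 2.58, 2.75 and 3.18, an increase of 7%, 14% and 32%. Small counts are the main source of noise, and persistent cases add to it.

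**The case against.** The strongest reply is that nothing turns on these rows. They carry no test, threshold or stopping rule, and the SAP and protocol agree with each other. Randomization balances pre-dose ideation in expectation, and the risk difference hardly moves. That stands, and it sets the weight of the point.

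Other safeguards also exist:

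- Exclusions 8 and 20, and the rule in protocol Section 5.3.1.1 that results at first dosing be clinically acceptable, would keep out some subjects with item 1-3 ideation. They make the 5% scenario less plausible.
- Worsening of an existing condition is an adverse event (protocol Section 6.1.1.1), and new or worsened ideation reported as one appears in the treatment-emergent tables.
- The DMC sees unblinded safety data (protocol Section 5.5.5).

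These cover the gap only in part. No rule bars item 1-3 ideation outright or makes an item 1-3 yes an adverse event automatically, and DMC access does not change the final tables. If the by-visit table includes pre-dose visits it would show group prevalence, but not change within a subject.

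A reader might infer that C-SSRS is the one safety variable in SAP Section 11 not referenced to baseline. That is too broad: the listings of flagged laboratory, vital-sign and ECG values take every qualifying observation at any time in the study.

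**Conclusion.** The point holds as a modest limit of a descriptive table. The item 1-3, ideation, ideation-only and ideation-or-behaviour rows cannot report how many subjects per arm had new or worsened ideation on drug. Rows for items 4-5 are largely unaffected, because those answers are screened out before dosing.

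A reader might go further and conclude that the comparison between arms is biased or that a suicidality signal would be hidden. The documents do not support that. The comparison of any post-dose ideation remains a valid randomized one. In the illustration, only the ratio read as new ideation is diluted, while the difference stays at 1.90 to 1.98 points against 2.0.

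The size is unknown. Every rate in the illustration is assumed, and with no pre-dose ideation nothing changes. The case for acting is that the data are already collected and the remedy follows the SAP's own practice for adverse events, flagged values and MRI lesions.

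**What to change.** In SAP Section 11.6.1:

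1. State that the whole-study summary uses only assessments after the first dose, and show pre-dose status in its own column.
2. Add a shift table by arm from pre-dose category to worst post-dose category (none, ideation items 1 to 5, behaviour). Give it rows for new ideation (none before, any after), worsened ideation (highest post-dose item above the pre-dose item) and new behaviour (none before, any after).
3. Use the SAP Section 6.2 baseline, the last value before the first dose, as the main reference. Flag ideation reported only at Screening or in the history separately.

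The third step matters. Exclusion 9 ties the Screening answers to the year before Screening. If the worst of Screening and Day 1 were the reference, and Screening carried that look-back, a subject with item 1 ideation months earlier, none on Day 1 and item 1 again on drug would be neither new nor worsened. Using the last pre-dose value counts the recurrence, and the flag keeps it visible as one.

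The cost is SAP wording and one extra descriptive table to program and read. Visits, sample size and error rates do not change.
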